## Aim 1 Statistical Analysis Plan

**Aim 1:** Assess impact of VBF-e on the use of medications.

**Study Design:** Difference in Differences

**Study Period:** Jan 1st, 2015 – December 31st, 2019

**Unit of Analysis:** per member month

**Analytic Sample:** Premera Blue Cross beneficiaries less than 65 years of age

**Censoring Events:**

*Month at which an individual:*

- disenrolled for more than 1 month during study period
- turned 65 years of age

*Administrative censoring at:*

- end of study period (December 31st, 2019)

*Administrative left truncation at:*

- 24 months prior to index date

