**Inclusion criteria:**

*Individuals:*

- aged 0-64
- Continuously enrolled in an employer-sponsored health plan for at least 12 months (with one-month allowable gap) prior to the index date
  - For individuals in the exposed group, the index date is defined as the start date of value-based formulary implementation at the employer group level
  - For individuals in the control group, the index date is defined as the index date of the matched exposed individual

*Employer groups:*

- that transition to the value-based formulary if they transitioned **all** enrollees in that employer group (no individual selection)

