**Covariates:**

*Adjustment variables:*

| Covariates   | Time of Measurement                     | Notes  | Specification  |
|--|---|--|--|
| Gender   | Month before E4 transition = index time |  | Indicator  |
| Age  | Index time                              | Centered   | Continuous   |
| Relationship to contract holder                        | Index time                              |  | Categorical 

• Contract Holder,

• Dependent,

• Spouse/Domestic Partner)

 |
| ACS  | Index time (or closest to this)         | For individuals with missing ACS variables at index time, set to closest observed value. | Quintile   |
| Percent 25 years old or older with a bachelor's degree |   |  | Quintile   |
| Median household income                                |   |  | Quintile   |
| Population size  |   |  | Quintile   |
| Percent White  |   |  | Quintile   |
| Funding Type   | Index time                              |  | Categorical (self, full)   |
| Elixhauser   | 12 months prior to transition time      |  | Categorical variable 

• 0

• 1

• >=2

                                  |
| Time from index date                                   | At all observations                     | 0 = index time, 1 = E4 transition month  | Continuous (-23 to 36)   |
| Post   | At all observations                     | Indicator for post period  | Indicator  |

|             |                     |   |   |
|-------------|---------------------|---|---|
| Seasonality | At all observations | Adjust for calendar year and separately adjust for calendar month | Categorical (1 through 12 for elig_mth) and (2015 through 2019 for elig_yr) |
|-------------|---------------------|---|---|

**Effect Modifiers:** None.

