**Statistical Analyses:**

We will use a DID approach to study the impact of the E4 transition and generalized linear models to model the impact of the E4 transition via changes in outcomes. Time will be anchored at the month prior to the transition (e.g., index time is set to the month prior to the transition) for the E4 group. Each of the E4 transition members will be matched to two controls via propensity score methods. Non-E4 transition members will be assigned to an index date corresponding to their E4 transition match. We will not adjust for the matching in our models.

To match controls to E4 members, we will model the propensity score based on covariates we believe may be related to exposure: Gender, ACS Population Size, ACS Household Income in past 12 months, ACS Percent 25 years and older with a Bachelor's degree, ACS Percent White, and Year of birth. Then, we will obtain the log odds (logit) of the fitted values (e.g., estimates) of the propensity score for everyone (both E4 and possible controls) and order the log odds of the treatment (E4) group from largest to smallest (in decreasing order). For each E4 member, we will find the two nearest neighbor controls, e.g., the controls with the closest propensity score to that of the E4 individual with 12 months of continuous prior enrollment at the E4 individual's index date. After completing matching, we will check for covariate balance across groups based on the standardized mean differences and Kolmogorov–Smirnov statistic.

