**Model:**

Denote spending for member  $i$  at time  $t$  as  $y_{it}$ , with  $i \in \{1, \dots, N\}$ ,  $t \in \{-23, \dots, 0, \dots, 36\}$ , and  $N$  the number of members. Let  $M$  be the number of covariates included in the model and  $x_{m,it}$  denote the  $m^{\text{th}}$  covariate for member  $i$  at month  $t$ .

Then the two-stage model is:

$$\begin{aligned} p_{it} &\sim \text{Bernoulli}(\theta_{it}), \\ \text{logit}(\theta_{it}) &= \alpha_0 + \sum_{m=1}^M \alpha_m x_{m,it}, \\ (y_{it} \mid y_{it} > 0) &\sim \text{Poisson}(\mu_{it}), \quad \text{and} \\ \mu_{it} &= E(y_{it} \mid y_{it} > 0, X_i), \end{aligned}$$

where  $X_i$  is the matrix for all observed covariates for member  $i$ . We model the mean,  $\mu_{it}$ , as

$$\log(\mu_{it}) = \beta_0 + \sum_{m=1}^M \beta_m x_{m,it}.$$

We suppose,

$$\begin{aligned} \sum_{m=1}^M \alpha_m x_{m,it} &= \alpha_1 E4_i + \alpha_2 post_{it} + \alpha_3 month_{it} + \alpha_4 E4_i * post_{it} + \alpha_5 E4_i * month_{it} + \\ &\quad \alpha_6 post_{it} * month_{it} + \alpha_7 E4_i * post_{it} * month_{it} + \alpha_8 Age_i + \\ &\quad \alpha_9 Gender_i + \alpha_{10} Elixhauser_i + \alpha_{11} Relationship_i + \\ &\quad \alpha_{12} FundingType_i + \alpha_{13} ACSPopulation_i + \alpha_{14} ACSIncome_i + \\ &\quad \alpha_{15} ACSPercentWhite_i + \alpha_{16} ACSEducation_i, \end{aligned}$$

and

$$\begin{aligned} \sum_{m=1}^M \beta_m x_{m,ijt} &= \beta_1 E4_i + \beta_2 post_{it} + \beta_3 month_{it} + \beta_4 E4_i * post_{it} + \beta_5 E4_i * month_{it} + \\ &\quad \beta_6 post_{it} * month_{it} + \beta_7 E4_i * post_{it} * month_{it} + \beta_8 Age_i + \\ &\quad \beta_9 Gender_i + \beta_{10} Elixhauser_i + \beta_{11} Relationship_i + \\ &\quad \beta_{12} FundingType_i + \beta_{13} ACSPopulation_i + \beta_{14} ACSIncome_i + \\ &\quad \beta_{15} ACSPercentWhite_i + \beta_{16} ACSEducation_i, \end{aligned}$$

for member  $i$  where:

- $E4_i$  = indicator of whether the  $i^{\text{th}}$  member is enrolled in VBF-E4
- $post_{it}$  = indicator of whether the  $i^{\text{th}}$  member is in the post index period,  $t \geq 1$
- $month_{it}$  = time in months from the  $i^{\text{th}}$  members index date
- $Age_i$  = centered age for the  $i^{\text{th}}$  member at index
- $Gender_i$  =  $i^{\text{th}}$  members gender at index
- $Elixhauser_i$  = Elixhauser comorbidity score for member  $i$  at index
- $Relationship_i$  =  $i^{\text{th}}$  members relationship to contract holder at index

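### The disenrolment censoring rule is not limited to time after index, so some eligible, matched members are censored before index and give no post-period data

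*SAP*

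**What the plan says.** Under Censoring Events, in identical words for Aims 1, 2 and 3, the SAP censors at the month in which a member "disenrolled for more than 1 month during study period". The study period is given at the head of each aim as "Jan 1 st , 2015 – December 31 st , 2019". It is a calendar window and is not tied to a member's index date. The same Censoring Events list places left truncation at "24 months prior to index date", and the model's time axis runs from t = -23 to t = 36, with the post period starting at t = 1.

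The Inclusion criteria require a member to be "Continuously enrolled in an employer-sponsored health plan for at least 12 months (with one-month allowable gap) prior to the index date". Statistical Analyses asks no more of controls, who are taken from those "with 12 months of continuous prior enrollment at the E4 individual's index date".

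Nothing in the SAP restricts the disenrolment event to time after index, restarts observation after re-enrolment, or begins observation at the start of the enrolment spell that contains the index date.

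**The concern.** About a year of the observed pre-period lies outside the enrolment requirement but inside the window in which disenrolment censors. A member can therefore pass eligibility, be matched, and then be censored by an old gap before index. Such a member supplies nothing to the primary outcome in any aim, the change in area under the curve in the year after index.

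Two consequences follow:

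- Post-period outcome data are lost for no analytic reason, because the member is enrolled at index and could be followed.
- The few months that remain sit at the early end of the linear pre-period trend. The early pre-period and the post-period then describe somewhat different members. The balance check, made once matching is complete, would still count people who have no post-period data.

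**Working it through.** No SAP figure is available to reproduce, so the check applies the SAP's own rules month by month.

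**Inputs.** Time axis: t = 0 is the month before transition and t = 1 is the transition month (Covariates). Observation opens at t = -23. Look-back is 12 months with one gap month allowed (Inclusion criteria). Disenrolment of more than one month censors anywhere in January 2015 to December 2019.

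**Worked example, transition in January 2017.**

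- t = 1 is January 2017, t = 0 is December 2016, and t = -23 is January 2015.
- The member is enrolled January to April 2015, out May to July 2015, and enrolled without a gap from August 2015.
- Continuous enrolment before transition, August 2015 to December 2016: 5 + 12 = 17 months. This is at least 12, so the member is eligible as an E4 member or as a control.
- The gap lasts three months and begins in May 2015, t = -19, inside the study period. The member is censored at t = -19.
- Months contributed as written: t = -23 to -20, which is 4. Post-period months: 0.
- If only disenrolment after index counted, and the member stayed enrolled to the end of 2019: 4 + 17 + 36 = 57 months. If observation also started at the current spell: 17 + 36 = 53 months.

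**Which gaps cause this.** Let the look-back begin at month w and the gap last L months from month s. Eligibility allows at most one gap month in the look-back, so the gap's last month, s + L - 1, must be no later than w. Hence s ≤ w - L + 1. The earliest observed start is t = -23.

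| Index and look-back | L = 2 | L = 3 | L = 6 |
|---|---|---|---|
| Index t = 0, look-back t = -12 to -1 | 13 to 23 | 14 to 23 | 17 to 23 |
| Index t = 0, look-back t = -11 to 0 | 12 to 23 | 13 to 23 | 16 to 23 |
| Index t = 1, look-back t = -11 to 0 | 13 to 24 | 14 to 24 | 17 to 24 |

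Entries are months before index at which the gap starts. The third row is needed because the Inclusion criteria put index at the formulary start, whereas Covariates and Statistical Analyses put it one month earlier. The range of 13 to 23 months is therefore approximate. In every cell censoring falls before t = 1, so post-period months are 0.

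**Can it occur within the calendar?**

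| January transition in | Study months up to t = 0 | Observed months at t = -23 to -12 | Study months before t = -23 | Post months available |
|---|---|---|---|---|
| 2016 | 12 | 0 | 0 | 48 (axis stops at 36) |
| 2017 | 24 | 12 | 0 | 36 |
| 2018 | 36 | 12 | 12 | 24 |
| 2019 | 48 | 12 | 24 | 12 |

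The problem cannot arise for a January 2016 transition and can arise for the other three. For 2018 and 2019, a gap in the study months before t = -23 would, on the literal rule, censor the member before observation opens and leave no data.

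**The case against.** The strongest reply is that this is loose wording. Censoring normally means an event that ends follow-up. The Censoring Events list deals with the early boundary separately, under left truncation, and its companion event, reaching age 65, can only end follow-up for someone eligible at index. On that reading the disenrolment rule acts from index onward and nothing is lost. This is probably what was meant. The text nevertheless ties the event to the calendar study period, and left truncation at 24 months puts the gap inside observed time. Even on the intended reading, the SAP does not settle whether months before an early gap are kept (57 months in the example) or dropped (53).

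Other parts of the reply stand, and they limit the point:

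- A reader might infer that losing one member of a 1:2 set damages the matched analysis. The SAP does not support this. It states that the models will not adjust for matching, the model equations contain no matched-set term, and the bootstrap clusters on the individual. Ordinary disenrolment after index breaks sets in the same way.
- A reader might infer a biased difference-in-differences estimate. The same rule applies to both groups, the gaps precede exposure, and the transition is made for whole employer groups. Bias would require gap-prone members to differ in frequency or in response between groups, and nothing in the SAP shows that.
- The membership of pre and post months already varies by design, since only 12 months of prior enrolment are required on an axis that opens at t = -23, and members leave after index.

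**Conclusion.** The point holds as a drafting defect that affects the primary-outcome dataset in all three aims. Followed literally, the rule removes every post-period month from eligible, matched members who had a gap of two or more months roughly 13 to 23 months before index, and it removes all data from those whose gap lies earlier but within the study period.

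The loss per affected member depends on the transition date and on continued enrolment. It is up to 36 post months for a transition by January 2017 and up to 12 for January 2019. The share of members affected equals the share with such a gap, which the SAP does not give; it gives no transition dates either. No percentage loss and no direction of bias can be claimed. Nor are the two rules logically incompatible, as a reader might infer: eligibility and censoring can both be applied, but together they discard usable follow-up. The correction is worth making because it is cheap and because the written rule yields a poorer dataset than the one probably intended.

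**What to change.** In Censoring Events for Aims 1, 2 and 3, change the event to: *first disenrolment of more than 1 month after the index date*. Use one definition of index throughout, because the Inclusion criteria and the Statistical Analyses section currently differ by a month. State how a gap that straddles index is counted.

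Optionally, add a sentence on earlier gaps: either months before such a gap are kept, or observation starts at the later of 24 months before index and the start of the enrolment spell containing index. The second choice is secondary to the main correction and costs a few early member-months (four in the example).

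The cost is one changed line per aim, one aligned definition, and the corresponding change to the data step that builds the member-month file.

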**Exclusion criteria:**

*Exclude individuals with:*

- missing gender information
- missing zip code level demographics at all member months

**Inclusion criteria:**

*Individuals:*

- aged 0-64
- Continuously enrolled in an employer-sponsored health plan for at least 12 months (with one-month allowable gap) prior to the index date
  - For individuals in the exposed group, the index date is defined as the start date of value-based formulary implementation at the employer group level
  - For individuals in the control group, the index date is defined as the index date of the matched exposed individual

*Employer groups:*

- that transition to the value-based formulary if they transitioned **all** enrollees in that employer group (no individual selection)

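### Does defining the index date as the formulary start put the first exposed month in the pre-period?

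*SAP*

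**What the plan says.** The same text appears in Aims 1, 2 and 3.

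- **Inclusion criteria.** For exposed members, "the index date is defined as the start date of value-based formulary implementation at the employer group level". A control takes the index date of the exposed match.
- **Statistical Analyses.** The time anchor is the month before: "index time is set to the month prior to the transition". For controls, "Non-E4 transition members will be assigned to an index date corresponding to their E4 transition match".
- **Covariates.** Index time is equated with the month before the transition. The row *Time from index date* is coded "0 = index time, 1 = E4 transition month", with range -23 to 36. The Elixhauser row uses a third expression, "12 months prior to transition time".
- **Model.** The month variable counts from the "members index date". The post indicator marks whether the "member is in the post index period", given as t ≥ 1.
- **Censoring Events.** Left truncation is at "24 months prior to index date".
- **Outcomes.** The primary outcome is the change in area under the curve over one year from the index date. The secondary outcomes use two and three years.

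**The concern.** Two terms that sound alike are attached to two different points, and the plan uses them side by side without saying how they relate. The only formal definition of *index date* is the formulary start. The Model section and the Outcomes section both refer to the index date, so a programmer working from those two places and the Inclusion criteria alone would subtract the start month from each calendar month. The transition month would then be t = 0 with post = 0, and the one-year window would hold exposure months 2 to 13. Controls inherit the date, so their axis would move as well.

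The term sets the window of the primary outcome in every aim. The model also has a separate pre-period slope for the E4 group. A single exposed month at the end of the pre-period has high leverage on that slope, and therefore on the projected counterfactual.

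**Working it through.** **Step 1: the stated axis.** The range -23 to 36 has 60 values: 24 at or below zero and 36 above it. With the Covariates coding, t = 0 is the month before the transition and t = 1 the transition month. All 24 pre-months are unexposed and all 36 post-months are exposed.

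**Step 2: both readings in calendar months.** The plan gives no start date, so take a start of 1 January 2017 as an assumption.

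| | Coding row (t = 0 is December 2016) | Start month taken as t = 0 (January 2017) |
|---|---|---|
| Transition month | t = 1, post = 1 | t = 0, post = 0 |
| Exposed months at t ≤ 0 | 0 | 1 |
| t = 1 to 12 | Jan to Dec 2017, exposure months 1–12 | Feb 2017 to Jan 2018, exposure months 2–13 |
| t = -23 to 36 | Jan 2015 to Dec 2019 | Feb 2015 to Jan 2020 |

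Under this start date the coding row fills the study period exactly, and the other reading runs one month past its end.

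**Step 3: can the definitions be reconciled?** Treat the start as a date, the first day of the transition month, so that it is the boundary between t = 0 and t = 1. Then:

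- 24 months before it are t = -23 to 0, which is the left end of the axis;
- 12 months of prior enrolment, and the Elixhauser look-back, are t = -11 to 0;
- one, two and three years after it are t = 1–12, 1–24 and 1–36.

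All of these match the axis as written. If the start month itself is t = 0, then 24 months earlier is t = -24, which is off the axis.

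**Step 4: the size if the coding row were ignored.** Use a linear analogue with separate straight lines before and after, and area change = post line minus extrapolated pre line over t = 1–12. For a constant effect of 1 unit per month, the share lost is the weight of the point t = 0 in the pre line projected to the window's midpoint, c = 6.5:

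w = 1/n + (c − t̄)(0 − t̄)/Sxx

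With n = 24 (t = -23 to 0), t̄ = -11.5 and Sxx = 24 × (24² − 1)/12 = 1150:

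w = 1/24 + (18 × 11.5)/1150 = 0.0417 + 0.1800 = 0.2217

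The one-year area is 12 × (1 − 0.2217) = 9.34, against 12.00 with the coding row.

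In the limiting case where every member has only the minimum 12 months plus the misplaced month, n = 13, t̄ = -6 and Sxx = 182:

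w = 1/13 + (12.5 × 6)/182 = 0.0769 + 0.4121 = 0.4890

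The direction is not fixed. For an effect that ramps up over 12 months and then stays level, with 36 post-months, the coding row gives 7.28 and the other reading 7.79, a ratio of 1.07. Both exceed the true one-year sum of 6.50 because one straight post line is fitted to a bent effect, which is a separate matter from the index.

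**The case for a change.** The best case for a change is that a clear table does not cancel a formal definition repeated in three aims. The Model and Outcomes sections name the index date, not the index time. The convention that reconciles the texts, with the start falling on the first of a month and months counted from 1, is nowhere stated. Ordinary subtraction of calendar months gives zero for the start month. A few words per aim would remove the doubt, and an error here would reach every primary result.

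Part of this stands: the plan does not say how its terms relate, and a reader has to work it out. The rest is weaker. The month variable in the Model section is the covariate *Time from index date*, on the same axis, and its row gives the value for the transition month outright. That coding does not depend on the first-of-month convention. The Statistical Analyses section repeats the same anchor in words. To reach the harmful reading, a programmer must pass over both and also accept an axis that no longer fits the plan's own truncation rule. A one-month shift in the enrolment look-back would matter little, since the rule already tolerates a one-month gap.

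**Conclusion.** The inconsistency of terms is real but clerical. The coding row and the time anchor, both present in all three aims, fix the transition month at t = 1 with post = 1, and the remaining windows follow once the start date is read as the boundary between t = 0 and t = 1. Tidier wording would leave the data, the model and the results as they are, so no change is called for.

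The 22% loss is conditional on ignoring the coding row. It also assumes a constant effect, a full 24-month pre-period for everyone and a linear scale, whereas the plan's models are two-part with logit and log links. The 49% figure is a limit in which nobody has more than the minimum look-back. The plan gives no distribution of pre-period lengths and no effect shape, so none of these figures estimates a bias in the planned analysis.

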**Outcomes:**

*Primary outcome(s):* change in area under the curve one year after index date for all outcomes

*Secondary outcome(s):* change in area under the curve 2 and 3 years after index date for all outcomes

*Actual outcome list:*

Days supply of medications.

**Exposure:** VBF-E4 and non-VBF-E4

**Covariates:**

*Adjustment variables:*

| Covariates   | Time of Measurement                     | Notes  | Specification  |
|--|---|--|--|
| Gender   | Month before E4 transition = index time |  | Indicator  |
| Age  | Index time                              | Centered   | Continuous   |
| Relationship to contract holder                        | Index time                              |  | Categorical 

• Contract Holder,

• Dependent,

• Spouse/Domestic Partner)

 |
| ACS  | Index time (or closest to this)         | For individuals with missing ACS variables at index time, set to closest observed value. | Quintile   |
| Percent 25 years old or older with a bachelor's degree |   |  | Quintile   |
| Median household income                                |   |  | Quintile   |
| Population size  |   |  | Quintile   |
| Percent White  |   |  | Quintile   |
| Funding Type   | Index time                              |  | Categorical (self, full)   |
| Elixhauser   | 12 months prior to transition time      |  | Categorical variable 

• 0

• 1

• >=2

                                  |
| Time from index date                                   | At all observations                     | 0 = index time, 1 = E4 transition month  | Continuous (-23 to 36)   |
| Post   | At all observations                     | Indicator for post period  | Indicator  |

|             |                     |   |   |
|-------------|---------------------|---|---|
| Seasonality | At all observations | Adjust for calendar year and separately adjust for calendar month | Categorical (1 through 12 for elig_mth) and (2015 through 2019 for elig_yr) |
|-------------|---------------------|---|---|

**Effect Modifiers:** None.

